## 2 Protocol Summary

Title:	Implementing a Skills Training Evidence-Based Treatment for Posttraumatic Stress Disorder (ISTEP)
Population:	Adult primary care patients with posttraumatic stress disorder symptoms, N=60
Intervention:	Behavioral health interventions, including web-administered and clinician administered brief Skills Training in Affective and Interpersonal Regulation (STAIR) for PTSD
Objectives:	Hybrid type 1 effectiveness-implementation trial to assess the feasibility, acceptability, and preliminary effectiveness of web-versus clinician-administered brief STAIR (primary outcome: PTSD symptoms, secondary outcome: functioning) while gathering information on implementation of both modalities. Findings will inform a full stepped-care approach to PTSD treatment that spans primary care and specialty care.
Design/Methodology:	60 patients were randomized, 30 in each condition (webSTAIR v. Brief STAIR). Participants completed study survey assessments at baseline (0 weeks), 15 weeks (active treatment), and 9-months post-randomization. To ensure consistency in timing of data collection, assessments are not linked to condition or amount of content completed.
Subject Participation Duration:	9 months

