### 5 Study Design

I-STEP is a single site, unmasked, hybrid type 1 effectiveness-implementation trial which will assess the feasibility, acceptability, and preliminary effectiveness of Brief STAIR and webSTAIR while gathering data on implementation. We will randomize 60 patients (30 in each condition). Participants will complete study survey assessments at baseline (0 weeks), 15 weeks (active treatment), and 9-months post-randomization (follow-up; see Figure 1). To ensure consistency in timing of data collection, assessments are not linked to condition or amount of content completed. We hypothesize that: 1) Brief STAIR and webSTAIR will be effective in reducing PTSD symptoms (primary effectiveness aim) and mental health symptoms (secondary effectiveness aim); 2) Brief STAIR (clinician-administered) will have advantages

over webSTAIR (self-directed) in terms of treatment completion; and 3) webSTAIR will evidence advantages over Brief STAIR in regard to scalability and sustainability. Outcomes will be assessed using survey data and chart extraction.

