# 7 Study Subject Selection

## 7.1 Subject Inclusion Criteria

To participate in research components, patients must endorse having experienced an event on the Life Events Checklist for the DSM-5 (LEC-5) and have elevated PTSD symptoms as measured by the PTSD Checklist for the DSM-5 (PCL-5), defined as reporting at least moderate severity of at least one question

1-5 and 6-7 and at least moderate severity on at least two questions 8-14 and 15-20. Additionally, participants must be over 18 years of age, able to engage in therapy in English.

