**Randomization procedure:** Participants will be randomized through a randomization software. Each patient will receive a unique study ID at the time of referral to the study that is not connected to identifiable data. Before randomization, the referred patient will complete the following enrollment procedures: (1) each referred patient will complete a clinical intake at with their IBH therapist, and (for those with PTSD treatment needs) give permission for study team to contact, (2) each referred patient will complete an assessment with study staff to determine eligibility for the study, (3) each referred patient will give study staff consent to participate in the study, and (4) each referred patient will complete the baseline assessments. Once a participant gives consent to enroll in the study, they will be provided with a unique ID number and this ID number will be connected to their identifiable data (access to identifiable data will be limited). Once all four steps of enrollment (clinical intake, eligibility assessment, consent, and baseline assessment) are completed, the participant will be randomized.

**Study design schedule:** This evaluation is designed so that all patients who may benefit from PTSD treatment will be offered STAIR through in-person/telehealth format. Only those who enroll in the study are randomized to webSTAIR will have access to the webSTAIR format. Group assignment will therefore be randomized for all eligible participants. We also acknowledge that, because clinic practices cannot change overnight, after STAIR is rolled-out, some patients still may not be provided STAIR, due to their treatment preference or their therapist's preference not to complete STAIR training. Therefore, even therapists who do not complete the STAIR training will be instructed to offer STAIR as an option that may be delivered by a different IBH therapist.

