## 15 Statistical Plan

### 15.1 Study Hypotheses

Hypotheses:

- A. Brief STAIR will lead to significant change PTSD symptoms between baseline and 3 months.
- B. WebSTAIR will lead to significant change PTSD symptoms between baseline and 3 months.
- C. There will be no group differences in change in PTSD across conditions.

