### 15.3 Statistical Methods

Analyses were conducted in SPSS version 29. All continuous outcome variables were evaluated for and met the assumptions of normality (using both the Shapiro-Wilk test and the test statistics for skewness and kurtosis) and homogeneity of variance (using Levene's test; Hahs-Vaughn & Lomax, 2020). Chi-square tests and independent samples t-tests were used to examine differences in study variables between participants assigned to STAIR and webSTAIR conditions. Paired samples t-tests were used to

examine pre to post differences and pre to follow-up differences; effect sizes were calculated using Cohen's d. Participant retention, measured by percent of intervention content completed, did not meet the assumption for normality. To compare differences in engagement between STAIR and webSTAIR, we used the Kruskal-Wallis test, a non-parametric test that does not assume distributions between groups are similar. Linear mixed models with repeated measurements nested within patients were used to examine changes in study outcomes across time points and between groups. We used the restricted maximum likelihood estimator and unstructured covariance matrices for residuals. We examined fixed effects of time, treatment group, and time by treatment group interactions for all study outcomes. In post hoc analyses, we used Spearman's correlations to examine the correlation between engagement and baseline trauma symptoms of discrimination, stigma, and attitudes toward help seeking. Post hoc LMMs examined primary outcomes only (PTSD symptoms, mental health symptoms, and depression symptoms) and included two indicators of engagement, percent of assigned intervention completed and additional contact hours (count of behavioral health encounters documented in the electronic medical records).

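### The between-arm mixed model gives each arm its own baseline mean, so its 15-week contrast is in effect a difference in mean change and forgoes the precision that baseline adjustment would add

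*Combined protocol and SAP*

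**What the plan says.** Section 15.3 describes the between-arm analysis as follows: "Linear mixed models with repeated measurements nested within patients were used to examine changes in study outcomes across time points and between groups". Estimation is by REML, with no structure imposed on the residual covariance. The fixed effects are then listed: "We examined fixed effects of time, treatment group, and time by treatment group interactions for all study outcomes". Section 5 sets the time points: "Participants will complete study survey assessments at baseline (0 weeks), 15 weeks (active treatment), and 9-months post-randomization". The between-arm hypothesis, C in Section 15.1, reads: "There will be no group differences in change in PTSD across conditions". Section 12 fixes the order of enrolment: "Once all four steps of enrollment (clinical intake, eligibility assessment, consent, and baseline assessment) are completed, the participant will be randomized". Section 2 gives the numbers: "60 patients were randomized, 30 in each condition".

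No section names a baseline covariate or a common-baseline constraint. The post hoc mixed models in Section 15.3 add only engagement indicators, and the independent-samples t-tests there are unadjusted too.

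**The concern.** The text does not say outright that baseline is a level of the time factor, but that is the natural reading of a model for changes across time points when assessments fall at baseline, 15 weeks and 9 months. Time, group and their interaction then give six free means, one per arm and visit, including two baseline means.

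Because baseline is measured before randomisation, the two true baseline means are equal. The second baseline parameter therefore describes nothing real. Estimating it makes the model subtract the whole of any chance baseline gap (a slope of 1), whatever slope the data support.

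Hypothesis C expects no difference between arms, so a non-significant result is only as informative as its confidence interval is narrow. Section 15.2 gives no SD, effect size or power to show that 30 per arm is enough for this comparison, and the baseline scores that could narrow the interval are already collected.

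**Working it through.** **Plan's own figure.** There is none to reproduce for this contrast. Section 15.2 calls 60 adequate without numerical inputs.

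**Inputs.** From the documents: n = 30 per arm, three visits, unstructured covariance, baseline before randomisation. Assumed: correlation ρ between baseline and follow-up of 0.4 to 0.7; k = baseline SD / follow-up SD of 0.7 to 1; follow-up SD (S) of 15 PCL-5 points; two-sided 5% level. Values of k below 1 are plausible for PCL-5 because Section 7.1 admits only patients with elevated scores, "defined as reporting at least moderate severity of at least one question" in specified item groups, which narrows the baseline spread.

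**Step 1: what the planned contrast estimates.** With complete data, six free means and an unstructured covariance, the fitted means are the observed arm-by-visit means. The 15-week interaction is then the difference in mean change. In simulated complete data the two agreed to about 2 × 10⁻¹⁵. With 25% missing at 15 weeks they differed by up to about 0.16 SD in a single data set, so the equality is then only approximate.

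**Step 2: how much of a chance baseline gap passes through.** For a baseline gap d, the expected follow-up gap is (ρ/k)d, so a share 1 − ρ/k of d enters the change contrast with its sign reversed. Over ρ = 0.4 to 0.7 the share is 30 to 60% at k = 1, 13 to 50% at k = 0.8 and 0 to 43% at k = 0.7.

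**Step 3: variances, complete data.**
- Planned: (2/n)·S²·(1 + k² − 2ρk)
- Baseline-adjusted: (2/n)·S²·(1 − ρ²)
- The bracketed terms differ by (k − ρ)², which is never negative and is zero when ρ = k.

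Ratio of adjusted to planned variance, with the equivalent increase in patients (1/ratio − 1) in brackets:

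| k | ρ = 0.4 | ρ = 0.5 | ρ = 0.6 | ρ = 0.7 |
|---|---|---|---|---|
| 1.0 | 0.700 (43%) | 0.750 (33%) | 0.800 (25%) | 0.850 (18%) |
| 0.9 | 0.771 (30%) | 0.824 (21%) | 0.877 (14%) | 0.927 (8%) |
| 0.8 | 0.840 (19%) | 0.893 (12%) | 0.941 (6%) | 0.981 (2%) |
| 0.7 | 0.903 (11%) | 0.949 (5%) | 0.985 (2%) | 1.000 (0%) |

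Generalised least squares information matrices for the six-mean and five-mean models give the same ratios.

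**Step 4: on the PCL-5 scale, ρ = 0.5.** Here (2/30) × 15² = 15.
- Planned SE: √(15 × 1.00) = 3.87 at k = 1; √(15 × 0.84) = 3.55 at k = 0.8; √(15 × 0.79) = 3.44 at k = 0.7.
- Adjusted SE: √(15 × 0.75) = 3.35.
- 95% half-width (1.96 × SE): ±7.6, ±7.0 or ±6.7 planned, against ±6.6 adjusted.
- Difference detectable with 80% power (2.80 × SE / 15): 0.72, 0.66 or 0.64 SD planned, against 0.63 SD adjusted.
- At k = 1, power for an assumed true difference of 0.5 SD rises from 49% to 61%.

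**Step 5: with dropout.** Assuming 24 per arm observed at 15 weeks and 22 at 9 months (monotone dropout), the 15-week gain is 14 to 34% (k = 1), 2 to 15% (k = 0.8) and 0 to 9% (k = 0.7). At 9 months it is 13 to 32%, 1 to 14% and 0 to 8%.

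**Step 6: small-sample cost.** Simulating covariate adjustment against change scores at 30 per arm (40,000 trials per cell, complete data) gave ratios, for ρ = 0.4/0.5/0.6/0.7, of 0.72/0.77/0.81/0.87 at k = 1, 0.85/0.91/0.96/1.00 at k = 0.8 and 0.92/0.96/1.00/1.02 at k = 0.7. Estimating the slope costs about 2% of variance, which leaves no net gain at k = 0.7 with ρ of 0.6 to 0.7.

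**Step 7: the other reading.** If baseline were left out of the model altogether, the planned contrast would ignore it. The ratio would be 1 − ρ², from 0.84 to 0.51, or 19 to 96% more patients. Adjustment helps on either reading.

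**The case against.** The planned model is standard and unbiased, and it estimates what hypothesis C names, a difference in change. The trial is framed as feasibility and preliminary effectiveness, its sample size rests on a pre-post comparison, and hypotheses A and B are untouched. The size of the gain is assumed and reaches zero. At ρ = 0.5 the half-width shrinks by about 0.4 points at k = 0.8 and 0.1 at k = 0.7, on a 0 to 80 scale. The plan states no equivalence margin, so no interval width could formally establish hypothesis C. Section 15.3 is in the past tense, so the change may come too late to be prospective.

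Much of this stands. There is no bias, and the PCL-5 gain may be small, since the entry threshold that narrows the baseline spread may also lower the correlation. The missing margin is a separate gap that adjustment does not close. If results are known, choosing between two adjusted models afterwards would add discretion, so one should be named before fitting.

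What does not follow is that the point can be left. The large-sample gain is never negative, the worst small-sample cost shown is about 2% of variance, and the data are in hand. BSI-18 and ISEL-12 have no entry threshold of their own, so k near 1 is easier to entertain for them.

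**Conclusion.** The concern holds. As written, the between-arm contrast is in effect a difference in mean change (exactly so with complete data), and the plan does not use the equality of baseline means that randomisation provides. The loss is one of efficiency. With complete data it equals 0 to 43% more patients over ρ = 0.4 to 0.7 and k = 0.7 to 1. The upper end needs equal SDs and the lowest correlation; the lower end arises when ρ is close to k. These figures assume ρ, k, the SD and the dropout, none of which the documents give. Confidence is high on the reading and the direction, and moderate on whether the gain will be material for PCL-5.

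**What to change.** Name one baseline-adjusted model for the between-arm estimate before fitting it:

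1. A constrained longitudinal model: time plus two explicit indicators, group at 15 weeks and group at 9 months (five mean parameters), keeping REML and the unstructured covariance. This stays closest to the present text.
2. A model of the 15-week and 9-month scores only, with baseline score and its interaction with time as covariates.

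For option 1, do not simply delete the group main effect. With time and group entered as factors, time plus time-by-group still has rank 6 and refits the planned model. Time plus the two post-baseline indicators has rank 5.

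Report the adjusted 15-week and 9-month differences with 95% confidence intervals for PCL-5, BSI-18 and ISEL-12. If outcome results are already known, keep the planned model, label the adjusted analysis post hoc and show both.

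The cost is about two sentences in Section 15.3 and two indicator variables, or one covariate with its time interaction. No new data are needed.

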### 3 Background/Rationale & Purpose

#### 3.1 Background Information

Provide background information, study rationale, and purpose / study objective(s) and/or hypotheses for this study. PTSD is a significant public health challenge that disproportionately affects individuals receiving care safety net hospitals. The lifetime prevalence of exposure to interpersonal violence among patients seen in safety net primary care and behavioral health clinics may be as high as 94%, with current diagnosis of PTSD ranging from 33% to 46%. Despite high rates of trauma and PTSD in these settings, PTSD is vastly under-recognized and under-treated, with only 13% of individuals with PTSD receiving any form of mental health treatment. Of those who do access treatment, only 57% receive a minimally adequate dose of psychotherapy (defined as at least 4 hours of therapist contact).

Racial, ethnic, and socioeconomic disparities in access to and retention in EBTs for PTSD can also be understood in terms of system- and client-level factors. At the system-level, low-income racial and ethnic minority individuals are more likely to live in neighborhoods with few mental health specialists. Further, providers in these settings have less access to specialized training in EBTs for PTSD, thereby rendering EBTs largely unavailable to clients. Clients in resource constricted communities are also more likely to access services through non-specialty primary care setting or community service agencies, and less likely to access specialty outpatient mental health services. These differences may reflect the pragmatic response to the low availability of mental health specialists and perceptions of lower quality of care, as well as consumer preferences for non-traditional mental health service settings. Preferences for informal support and non-specialty care may also be related to experiences of mental illness stigma and negative experiences with prior mental health treatment (including racial discrimination). The unavailability of EBTs for PTSD in usual care and underutilization of outpatient specialty care have led to concerning inequities in quality of care.

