#### 4.2.1 Primary Outcome Measures

**Feasibility and Acceptability.** We operationalized feasibility as participant retention and provider adherence to the protocol. Retention was calculated as the proportion of content for the assigned intervention that the participant completed (e.g., number of sessions [Brief STAIR] or number of modules [webSTAIR] completed / total number of sessions [5] or modules [10]). We utilized a researcher-developed fidelity checklist, adapted from the Brief STAIR fidelity checklist ([name] et al., 2002) to assess adherence to the intervention. Adherence is reported as percentage of session components delivered per protocol. Overall study fidelity was calculated at study completion based on adherence scores from a random 20% of Brief STAIR sessions. Fidelity was assessed by two raters. We assessed client acceptability (satisfaction) using The Client Satisfaction Questionnaire (CSQ-8, Larsen et al., 1979), an eight item self-report measure. Each item is scored on a 4-point Likert scale from 1 “poor” to 4 “excellent” to indicate level of satisfaction with services. Higher scores indicate greater satisfaction with services.

**Preliminary Effectiveness, PTSD Symptoms.** We use the PCL-5 to assess PTSD symptoms. The PCL-5 includes 20 items, which map onto DSM-5 criteria for PTSD. Items are scored on a 5-point Likert scale to indicate symptom severity (0 – not at all to 4 – extremely), with a possible total score of 0-80. A score  $\geq 33$  is considered clinically elevated.

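### The post hoc correlations of engagement with discrimination symptoms, stigma and help-seeking attitudes state no allowance for arm: if the arms are pooled, a completion gap shrinks them on average, and one overall coefficient cannot show an association that differs by format

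*Combined protocol and SAP*

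**What the plan says.** - **The analysis (Section 15.3).** One sentence, opening "In post hoc analyses, we used", gives Spearman correlations "to examine the correlation between engagement and baseline trauma symptoms of discrimination, stigma, and attitudes toward help seeking". It mentions no arm, stratum or adjustment. The same section does name treatment group in two other places: the Kruskal-Wallis comparison of engagement and the fixed effects of the mixed models.
- **The engagement measure (Section 4.2.1).** Retention is the proportion of assigned content completed: "number of sessions [Brief STAIR] or number of modules [webSTAIR] completed / total number of sessions [5] or modules [10". The sentence in Section 15.3 that follows the correlations uses two engagement indicators, percent completed and a count of other behavioural health contacts from the medical record. The correlation sentence does not say which one it means.
- **The expected direction (Section 5, hypothesis 2).** "Brief STAIR (clinician-administered) will have advantages" and, continuing, "over webSTAIR (self-directed) in terms of treatment completion". No size is given.
- **Numbers and timing.** Section 5: "We will randomize 60 patients (30 in each condition". Section 12 (randomisation procedure) places randomisation after the baseline assessment, so the correlates are fixed before arm is assigned.

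**The concern.** Attending therapist sessions and working through self-paced modules are different behaviours, counted in different units, and the plan expects one to be completed more fully than the other. If all 60 participants are ranked together, part of the spread in engagement is simply the arm difference. Randomisation makes that part unrelated, in expectation, to anything measured at baseline. It therefore adds noise and draws the coefficient towards zero.

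A second issue is independent of the first. If stigma, say, is related to session attendance but not to module completion, one overall coefficient reports an average that describes neither format. This can happen even when the arms complete equal proportions.

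At stake is how a small or null coefficient is read. These correlations are the plan's only stated look at whether the three baseline measures go with engagement. The later post hoc mixed models use engagement as a predictor of outcome, which is a different question.

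**Working it through.** **Plan's own figure.** The documents give no expected correlation, power or precision for this analysis. Section 15.2 supports N = 60 by naming a method without its inputs, so that number cannot be reproduced; nothing below depends on how it was derived.

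**Inputs from the documents.** 30 per arm; correlates measured before randomisation; completion in steps of one fifth or one tenth.

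**Assumptions not in the documents.** Two-sided alpha 0.05; no missing data; completion gap d from 0 to 2 within-arm SDs; within-arm correlation r up to 0.5.

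**Step 1: average shrinkage from pooling.** With 1:1 allocation, a gap of d within-arm SDs places each arm mean d/2 from the overall mean, so the pooled variance of engagement is 1 + d²/4 times the within-arm variance. The covariance with a baseline measure is unchanged in expectation. Hence r_pooled ≈ r_within / sqrt(1 + d²/4).

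| d | factor | loss |
|---|---|---|
| 0 | 1 | 0% |
| 0.5 | 1/√1.0625 = 0.970 | 3% |
| 0.8 | 1/√1.16 = 0.928 | 7% |
| 1.0 | 1/√1.25 = 0.894 | 11% |
| 1.5 | 1/√1.5625 = 0.800 | 20% |
| 2.0 | 1/√2 = 0.707 | 29% |

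**Step 2: simulation with stepped completion.** 2,500 runs per row, r = 0.4 in both arms. The stratified figure averages the two Fisher-transformed within-arm Spearman coefficients, using variance 1.06/(n − 3) in each arm.

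| d | mean pooled | mean stratified | power pooled | power stratified |
|---|---|---|---|---|
| 0 | 0.370 | 0.370 | 84.8% | 81.7% |
| 0.5 | 0.358 | 0.369 | 81.6% | 81.5% |
| 0.8 | 0.340 | 0.365 | 77.0% | 80.1% |
| 1.0 | 0.327 | 0.367 | 73.2% | 79.6% |
| 1.5 | 0.282 | 0.359 | 59.6% | 77.9% |

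The ratio of means at d = 1.0 is 0.327/0.367 = 0.89, as in Step 1. Ranking within arm before correlating, simulated separately, gives power against pooling of 84% v 85% with no gap, 84% v 83% at 0.5 SD, 84% v 75% at 1 SD and 83% v 62% at 1.5 SD. With no true association, rejection stays near 5% for either method.

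**Step 3: shrinkage is an average, not a certainty.** With continuous engagement and r = 0.4, the pooled coefficient was still the larger of the two in absolute size in 37% of runs at d = 0.5 and 26% at d = 1.0.

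**Step 4: associations that differ by format (continuous engagement).**
- r = 0.4 in one arm and −0.4 in the other: the pooled mean is about 0.00 and is rejected in 4-5% of runs at every gap, including zero. The stratified average does the same. A direct comparison of the two coefficients has about 83% power.
- r = 0.5 in one arm and 0 in the other, d = 0.8: pooled mean 0.22 with 38% power, stratified mean 0.25 with 46%, against 78% in the arm that has the association. With no gap, pooled power is still only 46%.

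**Step 5: what each arm can show alone.** The smallest correlation detectable with 80% power is tanh[(1.960 + 0.842) × sqrt(1.06/(n − 3))]. This is tanh(0.382) = 0.36 for n = 60 and tanh(0.555) = 0.50 for n = 30. At r = 0.4, simulated power in one arm is about 50-55%.

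**The case against.** The best defence is that the text is silent rather than wrong. One sentence on a post hoc analysis need not list every adjustment, and a reader who infers that the arms were certainly pooled goes further than Section 15.3 does. That stands. The gap to close is the missing statement, although naming treatment group elsewhere in the section and not here makes pooling the likelier reading.

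Second, the loss may be trivial. The documents never size the completion gap, and at 0.5 SD or less pooling costs about 3% of the coefficient and no meaningful power. A reader might infer that pooling weakens any association; it does so only on average, and only in proportion to the gap. This also stands.

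Third, engagement may mean the contact count instead of percent completed. Hypothesis 2 and the 5-versus-10 scoring do not apply to that indicator. This stands too, and is a reason to name the indicator.

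Fourth, it is tempting to cite Section 3.1 ("Preferences for informal support and non-specialty care may also be related to experiences of mental illness stigma") as evidence that stigma acts differently on the two formats. It is not: that passage contrasts informal and non-specialty care with specialty services, and both formats here are delivered within integrated primary care. A format-specific association is a possibility the analysis cannot show, not one the documents predict.

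Fifth, splitting by arm would be worse than pooling as the main analysis at a modest gap. The power figures bear this out, so the split should not lead. None of this removes the case for stating how arm is handled and accounting for it in the overall figure.

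**Conclusion.** The point holds as a minor matter of analysis and reporting. On the natural reading, the correlations combine two arms that the plan expects to differ in completion. The average loss runs from nothing to about 11% of the coefficient for gaps up to 1 SD, and to 20% at 1.5 SD. At an assumed within-arm r of 0.4 with stepped completion, that means power of 73% pooled against 80% stratified at 1 SD, and 60% against 78% at 1.5 SD. These sizes rest on assumed gaps and correlations.

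The inability to show a format-specific association is a separate limitation. It does not need a completion gap, and stratifying the overall figure does not cure it; only the by-arm display addresses it.

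A reader might also infer that these correlations determine who is offered which format. The documents give them no such role: they are labelled post hoc and appear in neither the listed outcomes nor the hypotheses. No primary or secondary conclusion changes.

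**What to change.** In Section 15.3, or in the report of results:

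1. State whether the arms were pooled.
2. Make the overall figure an arm-stratified Spearman over all 60: rank both engagement and the correlate within arm before correlating, or use a partial Spearman adjusting for arm.
3. Show the by-arm coefficients with 95% intervals as descriptive only, and note the power of about 50-55% per arm at r = 0.4, so that a null in one arm is not read as absence of an association.
4. State which engagement indicator each correlation uses.

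The cost is a short re-run on data already held. If completion turns out equal in the two arms, ranking within arm gives up about one point of power (84% v 85%). Averaging Fisher-transformed coefficients gives up about three (81.7% v 84.8% with stepped completion; 82.6% v 86.4% if engagement were continuous).
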